3.3 Secondary endpoints

- Quality of life
- Urinalysis and GFR determination [Time frame: 24 months]
- Assessment of PK/PD data of immunosuppressants level in plasma [Time frame: 24 months]
- Assessment of influence of outside temperature on sensitivity and efficacy of HEKcite device [Time frame: 24 months]
- Effects of immunosuppression weaning procedure on immunosuppression-related side effects (diabetes, hypertension, nephrotoxicity, hyperlipidemia) [Time frame: 24 months]

3.4 Trial Design

An prospective, monocenter, open label, one-arm, interventional trial to assess the safety and efficacy of the HEKcite therapeutic drug monitoring device is proposed.

flowchart of routine practice is presented in figure 1.

At time of first presentation at the University Hospital of Leuven, campus Gasthuisberg, more specifically at the department of nephrology (E409), a thorough clinical examination with urinalysis and a blood sample to examine the GFR value, is performed to confirm the diagnosis of end stage kidney disease (GFR < 15 ml/min/1.73 m²). Next, patients are informed about their clinical condition and the proposed treatment plan. After patients have provided their written informed consent, a preoperative plan is prepared.

All patients will be treated by the local team of abdominal transplantation surgeons and nephrologists from the University Hospital of Leuven, campus Gasthuisberg. The principal investigator will be responsible for the training of all investigators, to ensure rehabilitation according to the protocol.

Operation plan

When determined if a patient is eligible for both transplantation surgery and placement of the HEKcite device in the forearm, the operative plan is assessed. Kidney transplantation surgery cannot always be planned in advance. If a kidney donor graft is easily accessible, dates and other important data are planned and if not, these are planned as soon as a kidney donor graft becomes accessible. As previously described, the choice of surgical technique is the responsibility of the surgeons.

The preferred forearm for the HEKcite device is determined, in accordance with the patient and the surgeon. Standard protocol is to implant in the right forearm, but patient preference will be considered, as well as certain criteria (amputation, nerve deterioration, ...) that make these standards impossible.

Placement of the HEKcite device by making a medio-lateral incision of approximately 1.5 cm. Next, the device is placed subcutaneously, ensuring neovascularization around and 'through' the device

itself. The device is expected to be encapsulated by fibrin fibers, ensuring safe preservation in the forearm.

Clinical evaluation

- Urinalysis, GFR determination are the basic parameters to determine renal function. These tests will be evaluated every study visit. Also, PK/PD data of immunosuppressants will be checked with blood samples at every study visit. Furthermore, the temperature will be checked to evaluate the effect of the outside temperature on the vasodilatation and vasoconstriction of the microvessels surrounding the HEKcite device, and thus the sensitivity and efficacy of the HEKcite device will be assessed in these different temperature-related circumstances at every study visit. Measurements of the temperature will be done with the ROMED® thermometer in all cases to avoid intervariability between thermometers.

[figure not shown]

Figure 1: Flowchart routine practice

Abbreviations: ESRD: end-stage renal disease, KDQOL: kidney disease quality of life.

Postoperative complications

Since the choice for kidney transplantation depends largely on the patient condition, it is impossible to set one uniform surgical protocol.

Complications related to the transplantation surgery, the implant placement will be registered in the Case Report Form as serious adverse events (SAE) or adverse events (AE), according to the National Cancer Institute Common Toxicity Criteria for Adverse Events (NCI CTCAE) v4,0 guidelines (available from: http://evs.nci.nih.gov/ftp1/CTCAE/CTCAE_4.03_2010-0614_QuickReference_5x7.pdf) Since all interventions are part of routine practice, registration of (S)AEs in the CRF is considered sufficient, and no notification of SAEs will be made to the ethics committee. An AE is any undesirable experience associated with the medical intervention that results in:

- (1) Patient death;

- (2) Life threatening;
- (3) Requires patients hospitalization or prolonged hospitalization;
- (4) Results in a disability;
- (5) Results in permanent damage;
- (6) Results in congenital anomaly or birth defect.

Biological and mechanical stability of the HEKcite device

Biological and mechanical implant stability is determined through evaluation of the peri-implant infection rate, implant loss at routine consultations and at every study visit. In addition, long-term changes in biological and mechanical stability will also be examined clinically at 6 months after placement of the HEKcite device, and again at annual routine follow-up visits at 12 and 24 months.

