Purpose of clinical trial	
The purpose of this study is to assess accuracy and reliability of the HEKcite therapeutic drug monitoring device and compare these results with blood samples acquired at predetermined time points in kidney transplantation patients.
 
To date, only static data via blood samples is available, and too many grafts are rejected because of lack of dynamic measurements. This HEKcite biosensor provides a dynamic measurement device

	
which will improve drug compliance and the knowledge about receptor occupancy of therapeutic drugs in humans, and will eventually lead to fewer graft rejections, and thus better overall survival rates.

Primary objective	
Assessment of the accuracy and reliability of the monitoring device compared to reference standard of care blood values.

Secondary objective (s)	
To evaluate the mechanical stability of the HEKcite device To evaluate the biological stability of the HEKcite device after 6 months To evaluate the impact of the HEKcite device on drug compliance To evaluate the impact of the HEKcite device on graft functionality To evaluate the impact of the HEKcite device on patient' quality of life, assessed through KDQOL To evaluate the impact

Trial Design	
Open-label, interventional trial

Endpoints	
Graft survival [Time frame: 24 months] Urinalysis and GFR determination [Time frame: 24 months] Effects of immunosuppression weaning procedure on immunosuppression-related side effects (diabetes, hypertension, nephrotoxicity, hyperlipidemia) [Time frame: 24 months]

Sample Size	
50

Summary of eligibility criteria	
18 years to 75 years (adult, senior) Both sexes, no healthy volunteers

IMP, dosage and route of administration	Immunosuppressants, normal dosage, standard of care
Active comparator product(s)	None
Maximum duration of treatment of a Subject	24 months
Version and date of final protocol	20/09/2017
Version and date of protocol amendments	x

2. Background and rationale

3. Trial objectives and Design

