3.6 Trial Flowchart

	Screen visit	Surgery (day0)	Day1	Week 1	Week 6	Month 6 postop	12 months postop	24 months postop
Informed consent	X							
Physical examination	X	X	X	X	X	X	X	X
Transplant surgery		X						

Device implantation surgery		X						
Urinalysis	X	X	X	X	X	X	X	X
Blood samples to determine PK/PD	X (baseline)		X	X	X	X	X	X
GFR determination	X	X	X	X	X	X	X	X
Temperature control (ROMED®)	X (baseline)	X	X	X	X	X	X	X
Peri-implant infection rate			X	X	X	X	X	X

4. Selection and withdrawal of subjects

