6.2 Laboratory tests

Urinalysis, together with the blood samples for both the PK/PD data and the GFR rate will be tested preoperative to have a reference of respectively concentration of immunosuppressants and kidney function. Thus, the patients will give urine and with the dipstick method, the color and clarity will be assessed. For more specific results, a blood sample will also be drawn from the patient to test for GFR rates. The temperature of the patients will be evaluated using ROMED® thermometer at all visits, in order to evaluate longitudinal the effect of temperature on the sensitivity and efficacy of the HEKcite device.

6. Assessment of efficacy

Blood samples are standard of care assessments to evaluate the concentration of the immunosuppressants. We will compare these results with the information we get from the application that is connected to the HEKcite device.

7. Assessment of Safety

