8.3 Treatment stopping rules

8.4 Data monitoring committee (DMC)

Some indications for setting up a data monitoring committee:

- Life-threatening disease
- Patient population (e.g. pediatric population)
- Prior knowledge or strong suspicion that a treatment under consideration has the potential to harm patients
- Complex study design

For further information:

http://www.emea.europa.eu/docs/en_GB/document_library/Scientific_guideline/2009/09/WC500003635.pdf

8. Statistics

Wilcoxon-matched pairs test or repeated measures ANOVA will be applied to examine the evolution of QOL, assessed with the kidney disease quality of life (KDQOL), at respectively the two and three time-points for analysis of the primary endpoint hypothesis.

Statistical analysis will primarily consist of descriptive analysis. Wilcoxon-matched pairs test or repeated measures ANOVA will be applied to examine the evolution of different parameters at several time points. Regression analysis will be performed to examine the influence of different variables on biological and mechanical stability. All analysis will be performed using Prism® software (GraphPad Prism 5, Inc., La Jolla, CA) and SPSS software (version 21, IBM SPSS statistics, Chicago, IL).

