9.1 Sample size

At least 40 patients will be enrolled in this clinical trial to ensure strong statistical analysis.

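### Biological and mechanical stability are separate objectives but share the same two measures, infection and implant loss, neither of which is specific to mechanical failure

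*Protocol*

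**What the plan says.** The synopsis has a secondary objective "To evaluate the mechanical stability of the HEKcite device" and, as a separate item, one on biological stability after 6 months.

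Section 3.4 (paragraph on biological and mechanical stability) covers both together: "Biological and mechanical implant stability is determined through evaluation of the peri-implant infection rate, implant loss", at routine consultations and at every study visit. The next sentence adds that "long-term changes in biological and mechanical stability will also be examined clinically at 6 months after placement of the HEKcite device", and again at the annual visits at 12 and 24 months. It does not say what is examined or what counts as a failure.

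In the Trial Flowchart the only implant-specific follow-up row is "Peri-implant infection rate", from day 1 to 24 months. A physical examination is scheduled at every visit.

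Section 8 (Statistics) uses the outcome: "Regression analysis will be performed to examine the influence of different variables on biological and mechanical stability".

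Device readings come in elsewhere. Section 6 (Assessment of efficacy) says of the blood results: "We will compare these results with the information we get from the application that is connected to the HEKcite device". Section 3.4 also plans to study how temperature affects the device's performance.

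**The concern.** Two objectives that are listed separately should be answerable separately. With one shared pair of measures they are not. Infection says nothing about whether the device is structurally sound. Implant loss says so only if its cause is known, and the protocol does not ask for the cause. The failures most specific to an implanted sensor's mechanics, namely breakage and displacement in place, have no named measure.

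Three things are at stake:

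- The mechanical objective may be answered with a figure that reflects mainly infection.
- The planned regression cannot tell mechanical determinants from biological ones if both outcomes are the same variable.
- The accuracy comparison can use only devices that deliver a reading. Without a count of implanted devices that do not, the reader cannot judge how selective that comparison is.

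**Working it through.** The protocol gives no figure for stability, so there is nothing to reproduce. The check applies the two named measures to each possible state of a device at a visit. Implant loss is taken in its ordinary sense, that the device is no longer in place.

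| State of the device | Infection event | Loss event | Consequence for mechanical stability |
|---|---|---|---|
| In place, uninfected, intact, reading | no | no | No event; correct |
| In place, uninfected, fractured or displaced | no | no | No event; mechanical failure not registered |
| In place, uninfected, intact, not reading | no | no | No event; functional failure of unknown cause |
| In place, infected, intact | yes | no | Event, although nothing mechanical failed |
| Lost after a tissue reaction | yes or no | yes | Event with a biological cause |
| Lost for a mechanical cause | no | yes | Event, but not separable from the row above without the cause |

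Next, whether another part of the protocol fills the gap:

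- **Clinical examination at 6, 12 and 24 months (3.4).** It may find displacement or some structural failures. It has no criterion, and the device lies under the skin and is expected to become encapsulated (3.4, operation plan), so breakage or loss of signal need not be apparent.
- **Physical examination at every visit (flowchart).** It offers the occasion to check the implant, but nothing says that the check is made or recorded.
- **Adverse events.** Section 3.4 restricts these to six serious outcomes. Section 8.2.1 is broader but refers to medical occurrences in the patient. A device that fails without clinical harm fits neither clearly.
- **Device readings (section 6).** A silent device would appear as a missing pair in the comparison with blood values. No section turns that into a stability or function count.
- **Endpoints (3.2, 3.3 and synopsis).** No stability endpoint is listed that could supply another definition.
- **Regression (section 8).** If both outcomes are read from the same pair of measures, the dependent variable is the same and so are the fitted effects. Assigning infection to biological and loss to mechanical would separate them only in part: losses would still mix causes, and failures in place would still be absent.

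Illustration only. Take n = 50 implants (the synopsis sample size), and assume 2 infected or lost and f further devices that failed in place:

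- Event-free on the named measures: (50 − 2)/50 = 96%
- Free of any failure, (50 − 2 − f)/50:
  - f = 2: 46/50 = 92%
  - f = 5: 43/50 = 86%
  - f = 10: 38/50 = 76%

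The counts 2 and f are assumptions; the protocol gives no expected failure rate of any kind.

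**The case against.** The strongest reply is that infection and loss are not the whole measure, because the following sentence of 3.4 adds a clinical examination of stability. A reader might infer that a broken device is formally classed as mechanically stable, or that such failures are counted nowhere. The text supports neither. The protocol says that stability is evaluated through certain items; it does not say that absence of infection and loss means stable, and it defines no percentage. The examination could record some failures, and a silent device would leave a visible gap in the comparison with blood levels. This stands. What remains is that the examination has no criterion and that the named measures do not fit the mechanical objective.

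A missing flowchart row also does not prove that nothing is collected. The KDQOL questionnaire has no row but is collected at every visit (3.1, 6.1), and implant loss has no row although 3.4 assesses it at every visit. The case report form has sections on implant characteristics and annual follow-up whose fields are not shown. This stands too, and limits the claim to what the protocol specifies.

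Third, whether the device reads belongs to the primary objective of accuracy and reliability, and a reading may be lost for a biological reason, such as poor vascularization or vasoconstriction around the device, or through a fault in the application. This is right. A lost reading should not be equated with mechanical failure, and the fix keeps it apart.

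Finally, neither kind of stability is a listed endpoint and the analysis is mainly descriptive, so the effect on the trial's main conclusions is limited. That bears on the weight of the point. It does not turn it into a detail for an analysis plan: the protocol itself fixes the measures, and an analysis plan cannot recover integrity data that no visit was asked to collect.

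**Conclusion.** The point holds in limited form. Section 3.4 fixes one pair of measures for two separate objectives; the pair has no component specific to mechanical failure; and the added clinical examination has no failure criterion. As written, the mechanical objective cannot be answered apart from the biological one, and the regression in section 8 inherits the problem. This should be corrected, but it concerns a secondary objective and does not threaten the trial as a whole.

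The size is unknown. The gap between 96% and 92%, 86% or 76% shows only how the result would move under assumed counts. It is not an estimate of bias, because the protocol states no stability rate or threshold.

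The conclusion rests on reading implant loss as physical absence of the device. If loss of function was meant to be included, the protocol needs to say so. Even then, infection would remain a component of a measure labelled mechanical.

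**What to change.** In section 3.4, replace the joint definition with two:

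- **Biological stability:** no peri-implant infection, and no loss or removal for a tissue reaction.
- **Mechanical stability:** device in place, not displaced, and intact on the examination already scheduled.

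Record the cause of every implant loss, so that each loss counts under the right outcome.

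Add one flowchart row, with a matching case report form field, at each post-operative visit: implant present and intact; valid device reading (yes or no, with the cause if no).

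Report the proportion of all implanted devices that give a valid reading at each visit as a separate functional outcome beside the accuracy comparison. Give exact confidence intervals for this and for both stability rates. The denominator should be every device implanted, including those of subjects later withdrawn and replaced under section 5.4. Name the two stability outcomes separately in the regression in section 8.

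Reconcile the implant follow-up length when adding the row. Section 3.4 examines stability to 24 months. Sections 3.7 and 5.6 end implant-related parameters at one year, and they disagree with each other on biological implant safety (two years against one).

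The cost is one row and one tick box per visit, using examinations and application readings that are already planned. The reported stability rate may turn out less favourable.

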3.5 Study center

University Hospital Gasthuisberg (Leuven).

3.6 Patient population

All consenting patients that require major kidney transplantation surgery, and require immunosuppressive therapeutic drugs after surgery.

3.7 Duration

We aim to initiate the trial in November 2017 and estimate a total recruitment period of one year to include at least 50 and a maximum of 60 eligible patients in this monocenter trial. Quality of life, biological implant safety will be measured for two years after placement of the HEKcite device. Parameters related to implant will be assessed at routine follow-up consultation until one year after placement of the HEKcite device.

3.6 Trial Flowchart

	Screen visit	Surgery (day0)	Day1	Week 1	Week 6	Month 6 postop	12 months postop	24 months postop
Informed consent	X							
Physical examination	X	X	X	X	X	X	X	X
Transplant surgery		X						

Device implantation surgery		X						
Urinalysis	X	X	X	X	X	X	X	X
Blood samples to determine PK/PD	X (baseline)		X	X	X	X	X	X
GFR determination	X	X	X	X	X	X	X	X
Temperature control (ROMED®)	X (baseline)	X	X	X	X	X	X	X
Peri-implant infection rate			X	X	X	X	X	X

4. Selection and withdrawal of subjects

4.1 Inclusion criteria

- Requires transplantation surgery (heart surgery such as bypass is allowed at the same time);
- Legal age;
- Both female and male patients;
- Patients with histologically or clinically confirmation of (urgent) need for kidney transplantation surgery;
- Patients not eligible anymore for long-term conventional dialysis;
- Signed informed consent prior to surgery;
- Willing to complete all follow-up requirements.

5.2 Exclusion criteria

- Patients not eligible to the abovementioned criteria;
- Patients with medical contraindications for kidney transplantation surgery;
- Pregnant or nursing women;
- Have a history of transplantation surgery;
- Cannot return for required follow-up visits;
- Hypersensitivity to immunosuppressants;

- Acute preoperative neurological event (such as a stroke);
- History of substance abuse within one year or is a prison inmate;
- Participating in another study;
- Participation in a trial with an investigational product within the previous three months;
- Life expectancy less than five years.

5.3 Selection of participants

At time of confirmation of the need for kidney transplantation surgery, the local abdominal transplant surgeon and abdominal internist of the participating center in will consult whether the patient is indeed eligible for placement of the HEKcite therapeutic drug monitoring device. If the patients proves eligible, he/she will be informed or at least prior to the placement of the HEKcite device, the patient will be asked to give written informed consent for recording his/her data in the University Hospital Gasthuisberg Leuven database.

5.4 Withdrawal of subjects

Since the study comprises prospective collection of routinely-collected data in a database, no additional patient risk is expected. The in-house designed HEKcite protocol is based on the routinely-applied concept of implant loading, but consist of a custom-developed manufacturing process of the actual device. The anticipated side effects or toxicities are thus associated with the surgical placement of the device. They comprise postoperative complications at the transplantation site and device implant site (wound dehiscence, infection). The surgical techniques have been routinely carried out in transplant patients as standard of care in the University Hospital Leuven, campus Gasthuisberg.

Subjects are withdrawn from the clinical trial when they react allergic to the implantable device, when they suffer (Serious) Adverse Events, in case of poor compliance to the immunosuppressive therapy and in case of graft rejection. If withdrawal of the subject appears after screening but before surgical placement of the HEKcite device, the subject will be replaced. If withdrawal of the subject appears after surgical placement, the subject will also be replaced, but already received data will be used for statistical analysis. As the medical caretakers sees fit, poor compliance will also be a reason for withdrawal. In these cases the subject will be withdrawn and replaced, and the data will be used for statistical analysis.

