3.2 Primary endpoints

Graft survival [Time frame: 24 months]

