8.1 Specification, timing and recording of safety parameters

Preoperatively, standard of care will be provided to the subject, in order to determine safety. Patient will be informed about possible hazards. The surgery and extra implantation will once again be explained to ensure complete knowledge for the patient. Physical examination will be performed, together with urinalysis, baseline temperature, and baseline blood tests to determine GFR. These are all noted in the flowchart. During surgery itself, standard of care measurements will be provided and surgeon is allowed to take actions if any adverse reactions occur.

Postoperatively, standard of care measurements will be provided. Also, the patient will stay in the hospital as long as needed, as evaluated by the treating physician. Aside from the standard of care measurements, flow chart will be followed strictly in order to get the least variability in the study.

All adverse reactions are determined and reported to the appropriate regulations. If needed, patients can be excluded from the trial.

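### Section 5.4 withdraws and replaces implanted patients at outcome-related events and provides no follow-up afterwards, so the 24-month primary endpoint is informatively censored

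*Protocol*

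**What the plan says.** Section 5.4 lists the reasons for taking a subject out of the trial. Besides allergy to the device, subjects leave "when they suffer (Serious) Adverse Events, in case of poor compliance to the immunosuppressive therapy and in case of graft rejection". This is withdrawal from the trial, not only from use of the device.

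The same section then states: "If withdrawal of the subject appears after surgical placement, the subject will also be replaced, but already received data will be used for statistical analysis". On poor compliance left to the caretakers' judgement it adds: "In these cases the subject will be withdrawn and replaced, and the data will be used for statistical analysis". Nothing in the protocol describes visits or data collection after withdrawal.

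The events that trigger withdrawal are close to what the trial measures:

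- **Primary endpoint, section 3.2:** "Graft survival [Time frame: 24 months" (the time frame is 24 months).
- **Synopsis, secondary objectives:** "To evaluate the impact of the HEKcite device on drug compliance".
- **Section 3.4:** the one-arm trial is to assess safety as well as efficacy. Peri-implant infection and implant loss are checked at every study visit, and longer-term stability at 6, 12 and 24 months.
- **Section 3.3:** immunosuppression-related side effects (diabetes, hypertension, nephrotoxicity, hyperlipidaemia) and GFR over 24 months are secondary endpoints, as is quality of life.

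On adverse reactions, section 8.1 uses permissive wording: "If needed, patients can be excluded from the trial".

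**The concern.** A patient who rejects the graft, has a serious complication or stops taking the drugs is more likely than others to lose the graft later. If that patient leaves the trial at that point, whether follow-up continues depends on prognosis. Standard survival analysis assumes that censored patients have the same future risk as those still observed, and the rule in 5.4 breaks that assumption by design.

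The trial has one arm and no randomisation, so its results are absolute rates. Any distortion of those rates passes straight into the conclusion, and there is no comparator in which it might partly cancel.

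This is not something an analysis plan can settle alone. An analysis plan can say how withdrawn patients are counted, but it cannot supply follow-up that the protocol never collects.

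**Working it through.** **1. Triggers against outcomes.**

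| Trigger in 5.4 | What is kept | What is lost |
|---|---|---|
| Graft rejection | The rejection, and data before it | Later graft loss (primary endpoint), later GFR, later KDQOL |
| (Serious) adverse event | The event itself | Later or repeat events; for an implant infection, the remaining stability checks at 6, 12 and 24 months |
| Poor compliance | The lapse itself | Later compliance and its effect on the graft |

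How often the adverse-event trigger fires is unclear. Section 3.4 describes an adverse event by serious consequences, whereas section 8.2.1 covers any untoward medical occurrence. Under the wider definition, a new case of one of the side effects listed in 3.3 would itself trigger withdrawal.

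The KDQOL analysis is affected too. A matched-pairs test, named in the Statistics section, uses only patients with both measurements, so those withdrawn before the later visit drop out.

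**2. Size for graft survival.** The protocol gives no event, rejection or dropout rate, so there is no stated figure to reproduce. All rates below are assumptions:

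- w = share of implanted patients withdrawn for rejection: 10%, 20%, 30%
- L = graft loss by month 24 after rejection: 10% or 50%
- graft loss in all other patients: 2%
- no graft loss before withdrawal among those withdrawn

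True survival: S = 1 − [w·L + (1 − w)·0.02].

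Three ways to count withdrawn patients:

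- **A. Completers only, or idealised censoring at withdrawal:** 1 − 0.02 = 98.0%. Error A − S = w·(L − 0.02).
- **B. All implanted, with unseen later losses treated as survival:** 1 − (1 − w)·0.02. Error B − S = w·L.
- **C. Every withdrawal counted as graft failure:** (1 − w)·0.98. Error C − S = −w·(1 − L).

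Example, w = 30% and L = 50%: S = 1 − (0.15 + 0.014) = 83.6%. A is 98.0% (+14.4 points), B is 98.6% (+15.0) and C is 68.6% (−15.0).

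| w | L | True S | A (error) | B (error) | C (error) |
|---|---|---|---|---|---|
| 10% | 10% | 97.2% | 98.0% (+0.8) | 98.2% (+1.0) | 88.2% (−9.0) |
| 10% | 50% | 93.2% | 98.0% (+4.8) | 98.2% (+5.0) | 88.2% (−5.0) |
| 20% | 10% | 96.4% | 98.0% (+1.6) | 98.4% (+2.0) | 78.4% (−18.0) |
| 20% | 50% | 88.4% | 98.0% (+9.6) | 98.4% (+10.0) | 78.4% (−10.0) |
| 30% | 10% | 95.6% | 98.0% (+2.4) | 98.6% (+3.0) | 68.6% (−27.0) |
| 30% | 50% | 83.6% | 98.0% (+14.4) | 98.6% (+15.0) | 68.6% (−15.0) |

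Under A the error is zero only when L = 2%, that is, when withdrawn patients lose grafts at the same rate as the rest. The result depends on L as much as on w.

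**3. Wording to reconcile.** Section 5.4 states withdrawal for (serious) adverse events as a rule; section 8.1 makes exclusion a possibility. Within 5.4, poor compliance is first a fixed reason for withdrawal and then a matter of the caretakers' judgement.

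**The case against.** The strongest reply is that the triggering event is not lost. Section 5.4 keeps the data gathered before withdrawal, so the first rejection, the first adverse event and the lapse in compliance can all be counted. That stands. A reader might infer that every safety and compliance result is biased; the text does not support so broad a claim. What is lost is everything after the trigger.

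The second reply concerns direction. A reader might infer that the rule always favours the device. The protocol defines neither rejection nor graft survival, and the synopsis uses rejection loosely for graft failure. If rejection is itself counted as the primary event, that trigger coincides with the endpoint and does not inflate survival. If every withdrawal is counted as failure, survival is understated (column C). This also stands: direction depends on terms the protocol leaves open. The adverse-event and compliance triggers would still cut follow-up short in a prognosis-dependent way.

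Two further inferences are not supported:

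- **Conflict with the enrolment cap.** Section 3.7 plans "to include at least 50 and a maximum of 60 eligible patients in this monocenter trial", and 5.4 sets no limit on replacement. A conflict would need a required number of completers. No section states one, and section 9.1 asks only for at least 40 enrolled.
- **Bias in device accuracy.** Accuracy is judged by comparing device readings with blood values, and pairs obtained before withdrawal are kept. Nothing shows that agreement would look better because of the rule.

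Nor is 8.1 a flat contradiction. It does not say that exclusion happens only when needed; the two sections differ in force and must be aligned.

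**Conclusion.** The point holds. As written, section 5.4 ends observation at events that are outcomes or lead directly to them, and replaces implanted patients with others who have not yet had such an event. Follow-up for 24-month graft survival is therefore informatively censored, and later GFR, KDQOL, adverse events and implant stability are missing for the same patients.

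Under the assumed rates, graft survival is overstated by 0.8 to 14.4 points with censoring or completers only, and by 1.0 to 15.0 points if unseen losses are treated as survival: about 1 to 15 points in all. It is understated by 5 to 27 points if every withdrawal is counted as failure. None of these rates comes from the protocol, and the low end needs only modest excess risk after rejection. The existence of the problem does not rest on them; it follows from the rule unless withdrawn patients have the same later risk as the others. It should be corrected before enrolment, because follow-up not collected under the rule may not be recoverable.

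**What to change.** Amend section 5.4 as follows:

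1. Separate stopping the device or a treatment, which stays with the treating team, from ending data collection.
2. Record rejection, (serious) adverse events, poor compliance and device removal as outcomes, with dates.
3. Follow every implanted patient to month 24 on the existing visit schedule unless consent is withdrawn.
4. Restrict replacement to patients who drop out before implantation.
5. Define the main analysis set as all implanted patients.
6. Reconcile the withdrawal rule in 5.4 with the permissive wording in 8.1, and the two statements on poor compliance within 5.4. Which clinical rule should apply is for the investigators.

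The cost is amendment wording and a little extra data collection for patients who would otherwise have left. Section 6.1 says that visits after screening follow standard post-transplant care, so most of these visits would take place anyway.
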